11.10. Exploratory Biomarkers

For subjects who provide separate consent and/or assent, blood samples for clinical research into exploratory biomarkers that have not been pre-identified will be collected, processed, and shipped to central laboratory for storage and/or analysis (including any future analysis). The date and time of collection will be captured. Reference the Laboratory Manual for additional details regarding the collection, processing, storage, and shipping of biomarker samples.

12. OTHER TRIAL ASSESSMENTS

Other trial assessments will be performed as indicated in [Table 3](#).

12.1. Demographics & Baseline Characteristics

For all subjects screened, date of birth, ethnicity, race, and dystrophin mutation type and analytical method will be captured.

12.2. Medical Status Questionnaire

Subjects will be evaluated for the following at screening and throughout the course of the trial:

- Frequency of manual/power wheelchair use
- Age permanently transitioned to a wheelchair full time
- Ventilatory support
- Frequency of falls

Changes in ambulatory status (i.e., transition from ambulatory to non-ambulatory) will be evaluated by a subject's performance in the 10MWR as part of the NSAA.

12.3. Medical History

Relevant and significant medical/surgical history will be collected at Screening and updated at Baseline.

12.4. Prior and Concomitant Medications

All medications taken within one month prior to the screening visit through trial completion will be captured. Medications will be reviewed at each trial visit and any medication changes, including new and discontinuations, will be recorded.

For each medication, generic name, indication, dose, frequency, route, and starting and stopping dates/times (if applicable) will be collected. The trade name of the medication is to be reported for combination therapies (e.g., Alka-Seltzer, Advair, etc.).

12.5. Planned Medical/Surgical Procedures

Data associated with any elective medical and/or surgical procedure (e.g., wisdom tooth extraction) that is not the result of an adverse event will also be captured.

For each procedure, the type of procedure, indication, and start date/time will be recorded. Any administered medication(s) related to the planned medical/surgical procedure(s) will be captured as a concomitant medication.

12.6. DMD Genetic Mutation Testing

DMD genetic testing will be available at screening for subjects who have not previously completed genetic testing or whose historical genetic results were not performed at a CLIA-certified laboratory as determined by an Investigator. The need for genetic testing should be assessed early

in the screening process, and if required, initial screening should be limited to genetic testing only since the turn-around time for final results may exceed the normal 30-day screening window.

Blood samples for DMD genetic testing will be collected and analyzed at a CLIA-certified central laboratory. Allow 29 to 49 days for receipt of test results.

13. ASSESSMENT OF SAFETY

13.1. Safety Parameters

Safety assessments will be performed as indicated in [Table 3](#).

13.1.1. Vital Signs

Heart rate, systolic and diastolic blood pressure, respiratory rate, body temperature, and blood oxygen saturation (SpO_2) will be measured after the subject has rested for approximately 5 minutes and before performing ECG and spirometry testing. A single set of values will be captured.

A subject's SpO_2 will be monitored for at least 30 minutes following each IP infusion (see [Section 10.8](#)).

Vital signs will be performed using equipment provided by investigative sites that has been properly calibrated per institutional guidelines.

13.1.2. Weight and Height

Weight, ulna length, and standing height measurements will be performed.

Investigative sites will make every effort to perform a weight measurement without the subject's wheelchair or other assistive device (e.g., walker), if applicable.

Ulna length will be measured in all subjects. Standing height will be measured if a subject is capable. If standing height cannot be measured, height will be calculated using the subject's ulna length ([Gauld et al., 2004](#)). It is critical to reduce variability in ulna length and standing height measurements across investigative sites. Therefore, site personnel must complete trial-specific training prior to measuring a subject's ulna length and standing height.

Table 5: Height Calculation from Ulna Length

$$\begin{aligned}\text{Height (cm)} = & [4.605 \times \text{Ulna Length (cm)}] \\ & + [1.308 \times \text{Age (years)}] \\ & + 28.003\end{aligned}$$

Centimeter and year entries must include decimal places. If a subject is 18 years or older, enter "18" in the formula for age.

13.1.3. Physical Examination

The physical exam (PE) is not considered a standard of care assessment as the examiner will be assessing for research events. Therefore, the physical exam is to be conducted only by an Investigator, or designated site personnel (e.g., nurse practitioners, physician assistants, research fellows) listed on the Delegation of Authority Log.

The physical examination will be a review of the major organ systems including: general appearance, HEENT, lymphatic, respiratory, cardiovascular, chest, abdomen, gastrointestinal, and musculoskeletal.

Clinically significant findings prior to investigational product administration are to be captured as medical history.

Clinically significant findings after the start of investigational product administration are captured and reported as AEs, if they meet the definition of an AE per Section [13.2.1](#).

13.1.4. Electrocardiogram (ECG)

All ECG measurements will be obtained in the supine position with standardized equipment that meet institutional standards for clinical use. Site personnel must complete trial-specific training prior to ECG measurements. A 12-lead ECG measurement and rhythm strip (10 seconds) will be obtained after measurement of vital signs and before spirometry testing.

The Investigator, a designated Sub-Investigator, or other appropriately trained site personnel will be responsible for performing 12-lead ECG assessments. The Investigator must provide his/her dated signature on the original paper tracing, attesting to the authenticity of the ECG machine interpretation, or their over-read and reinterpretation.

ECG data will be electronically transmitted to an independent cardiologist, contracted by Capricor, and evaluated. The independent cardiologist, blinded to treatment assignment, will conduct an over-read of the ECG measurements required for the trial. Investigative sites will receive a report with the independent cardiologist's ECG interpretations that must be reviewed, signed, and dated by an Investigator.

13.1.5. Immunologic Assessments

Serum for DSA testing and whole blood for HLA typing will be collected at each site at baseline, and then shipped to a central laboratory for analysis (See Laboratory Manual for shipping instructions).

DSA collections at the Week 4 (± 7 days) visit and 14-30 days prior to the planned date of the second, third, and fourth IP infusions will be assessed to determine MCB lot compatibility. These follow-up collections will occur either at the investigative site or remotely at a designated central laboratory patient service center.

DSA samples may also be collected in the setting of clinical suspicion of immune sensitization syndrome in the judgment of the Investigator. See Section [7.2.1](#) for additional details regarding immune sensitization syndrome as a safety endpoint.

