 - Immune sensitization syndrome shall be defined as: (a) clinical signs and symptoms consistent with systemic inflammation (e.g., fever, leukocytosis, rash, or arthralgia) with onset ≥ 24 hours post infusion and the absence of clinical signs of concomitant infection, **AND** (b) elevation of anti-human leukocyte antigen (HLA) antibodies against the donor cells (i.e., DSAs), detected ≤ 30 days following onset of syndrome, of (i) ≥ 2000 mean fluorescent intensity (MFI) if baseline MFI ≤ 1000 , or (ii) ≥ 2 times baseline otherwise

The **primary efficacy endpoint** is change from baseline to the 12-month timepoint in functional capacity as assessed by the mid-level (elbow) dimension of the PUL 1.2.

The **secondary safety endpoint** is the incidence and severity of all adverse events through the 12-month timepoint.

The **secondary efficacy endpoints** include the change from baseline for the following:

- Mid-level (elbow) dimension of the PUL 1.2 at Months 3, 6, and 9 (*Month 12 is the primary endpoint*)
- Regional systolic left ventricular (LV) wall thickening as assessed by cardiac magnetic resonance imaging (MRI) at Months 6 and 12

The **exploratory efficacy endpoints** include the change from baseline to each assessment timepoint for the following assessments:

- All subjects
 - High-level (shoulder) dimension of the PUL 1.2
 - High-level (shoulder) dimension of the PUL 2.0
 - Mid-level (elbow) dimension of the PUL 2.0
 - Distal-level (wrist and hand) dimension of the PUL 1.2
 - Distal-level (wrist and hand) dimension of the PUL 2.0
 - Grip strength
 - Key and tip-to-tip pinch strength
 - Elbow flexion strength
 - Slow vital capacity (SVC), forced expiratory volume in one second (FEV₁), forced vital capacity (FVC), peak expiratory flow (PEF), maximum inspiratory pressure (MIP), maximum expiratory pressure (MEP), peak cough flow (PCF), and inspiratory flow reserve (IFR)
 - LV structure and function as assessed by cardiac MRI including ejection fraction, end-diastolic volume, end-systolic volume, stroke volume, regional wall thickness, and circumferential strain

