All IV infusions will be conducted in an outpatient setting at the investigative site on Day 1 and Months 3, 6, and 9. Prior to each IP infusion, medication(s) will be administered to the subject as determined by the Investigator based on the pre-treatment guidelines (see [Section 21.2](#)) and/or institutional protocols to minimize the risk of potential severe allergic reactions such as anaphylaxis. Subjects will be observed in the outpatient setting for at least two hours post infusion and then discharged the same day if medically cleared by the site Investigator. As part of these visits, subjects will complete a safety phone call 14 days (\pm 3 days) after each IP infusion, and if clinically indicated, an unscheduled in-person visit will be performed at the investigative site with targeted assessments based on presentation of signs and symptoms.

Blood samples for DSA testing will be collected at Baseline, Week 4, 14-30 days prior to the IP infusions scheduled for the Month 3, 6 and 9 visits, and Month 12. Blood collections for clinical laboratory and DSA testing at Week 4 and pre-dose DSA testing at Months 3, 6, and 9 will occur either at the investigative site or remotely at a designated central laboratory patient service center. Blood collection for biomarker and exploratory biomarker testing at Week 6 and Month 4.5 will be conducted for those subjects who are able to travel to the investigative site.

If trial evidence suggests an appropriate risk/benefit profile of CAP-1002, Capricor, upon the recommendation of the Data Safety Monitoring Board (DSMB), may introduce an open-label extension study to offer CAP-1002 to subjects who were randomized to placebo and completed the 12-month follow-up period of the original trial.

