10.8. Post-Infusion Monitoring

Subjects will remain in the outpatient setting for at least 2 hours post infusion for observation, for longer should that be warranted in the judgement of the treating clinician. Investigative sites will observe their local institutional policies for post parenteral infusion monitoring. The subject's pulse oximetry (SpO₂) will be monitored for at least 30 minutes post infusion. A site Investigator will assess the subject for adverse events and approve his discharge the same day if medically cleared.

10.9. 14-Day Post-Infusion Monitoring

Subjects will complete a safety, follow-up phone call 14 days (± 3 days) after each IP infusion to document subject-reported AEs and new concomitant medications.

If clinically indicated, an unscheduled in-person visit will be performed at the investigative site with targeted assessments based on presentation of signs and symptoms of the subject.

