15.2. Clinical Events Committee (CEC)

The purpose of CEC adjudication is to provide consistent and unbiased adjudication of clinical outcomes and specified events through the independent review of source documentation. The charge of the CEC is to review source documents and to adjudicate the classifications of all potential primary safety endpoint events. Sites will be provided instructions in the MOP on how to collect and submit event information required for CEC review. The CEC will remain blinded to subject treatment assignments. The individuals that serve on the committee will be appointed by Capricor, are independent from all other trial activities, and are not affiliated with any investigative site. The committee will consist of, at a minimum, a neurologist and pulmonologist with experience in treating patients with DMD. Additional experts in immunology will be consultants to the committee as necessary. The frequency of CEC meetings is detailed in the CEC Charter.

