5.7 Donor-Specific Antibodies

Donor, donor profiles, allele, HLA, HLA Class and MFI will be listed by subject and visit. Subject HLA profiles will be provided in a separate listing.

DSA data will be analyzed in the context of immune sensitization syndrome should there be an occurrence.

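### For early onset after infusions 2-4, the DSA rise that defines immune sensitization syndrome depends on a for-cause sample that Protocol 13.1.5 leaves optional

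*Protocol*

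**What the plan says.** The Protocol Synopsis, Protocol 7.2.1 and SAP 2.2.1 define the syndrome in two parts, both required. Part (a) is clinical signs of systemic inflammation starting at least 24 hours after an infusion, without signs of infection. Part (b) is a DSA elevation "detected ≤ 30 days following onset of syndrome": at least 2000 MFI if baseline was 1000 or less, otherwise at least twice baseline. No upper limit is set on the time from infusion to onset.

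Protocol 7.1 schedules DSA samples at Baseline, Week 4, "14-30 days prior to the IP infusions scheduled for the Month 3, 6 and 9 visits, and Month 12". Protocol 13.1.5 says that the Week 4 and pre-infusion samples "will be assessed to determine MCB lot compatibility". It then adds the for-cause sample: "DSA samples may also be collected in the setting of clinical suspicion of immune sensitization syndrome in the judgment of the Investigator". The next sentence points to 7.2.1 for "additional details regarding immune sensitization syndrome as a safety endpoint", and 7.2.1 is where the 30-day limit is written.

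The scheduled contact soon after each infusion is the 14-day call (Protocol 10.9), made "to document subject-reported AEs and new concomitant medications". If clinically indicated, an unscheduled site visit with targeted assessments follows. That visit is worded as mandatory, but DSA is not named among its assessments. Month 4.5 blood is for biomarkers only.

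On reporting, SAP 5.7 states: "Donor, donor profiles, allele, HLA, HLA Class and MFI will be listed by subject and visit". It plans a DSA analysis only if a syndrome occurs.

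**The concern.** The definition needs a blood sample in a fixed window after onset, but the follow-up sampling schedule was built around donor-lot compatibility for the next infusion. The Week 4 draw happens to serve both purposes after infusion 1. Infusions 2, 3 and 4 have no equivalent draw. A case with compatible signs but no sample inside 30 days cannot satisfy part (b), so it is not counted as the syndrome.

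This matters because Protocol 5.6.3 names the immune response to repeated allogeneic doses as a safety question, and the gap falls on the repeat doses. Protocol 13.2.1.3 says that subjects will be monitored for immune sensitization through Table 3, but Table 3 does not supply the sample that the definition needs for early onset after those doses. If no syndrome is recorded, the visible SAP text triggers no DSA analysis either.

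**Working it through.** The plan states no figure on this point, so there is none to reproduce. The check is calendar arithmetic.

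**Inputs** (Protocol 7.1, Table 3, 13.1.5): infusions on Days 1, 90, 180 and 270, with ±14 days for infusions 2-4; Week 4 at Day 30 ±7; pre-infusion draw 14-30 days before the next infusion; Month 12 at Day 360 ±14.

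**Rule.** Onset k days after an infusion is covered if a scheduled draw falls at g days after that infusion with k ≤ g ≤ k + 30. The earliest onset a draw can cover is therefore g − 30.

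**Days from infusion to next scheduled draw**

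- Infusion 1, Week 4 draw: nominal 30 − 1 = 29, range 22 to 36. At 29 it covers onset days 1-29.
- Infusions 2 and 3: nominal 90 − 30 = 60 to 90 − 14 = 76. The earliest covered onset is day 30 if the draw is at 60, or day 46 if it is at 76. Window extremes: (180 − 14) − (90 + 14) − 30 = 32 and (180 + 14) − (90 − 14) − 14 = 104. At 32, onset on day 2 could be covered, but only with every window at its limit.
- Infusion 4: nominal 360 − 270 = 90, so the earliest covered onset is day 60. Window extremes: 346 − 284 = 62 and 374 − 256 = 118. Even at 62 nothing before day 32 is covered.

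These bounds need no distributional assumption.

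**Coverage over the visit windows.** The shares below count every integer-day combination equally: 15 × 29 × 17 for infusion 1 (including the draw before infusion 2), 29 × 29 × 17 for infusions 2-3, and 29 × 29 for infusion 4. Onset days are averaged equally within each range. Infusions are taken as given on the planned date; for-cause and early-termination draws are left out.

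| Onset days | Infusion 1 | Infusions 2-3 | Infusion 4 |
|---|---|---|---|
| 1-14 | 92.9% | 0.9% | 0% |
| 1-30 | 90.3% | 8.1% | 0% |
| 31-60 | 72.8% | 61.9% | 17.8% |
| 1-60 | 81.6% | 35.0% | 8.9% |
| 31-89 | 51.2% | 48.1% | 43.5% |

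**Checks by hand**

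- Onset day 14 after infusion 2 or 3 needs g ≤ 44. That occurs in 1 + 3 + 6 + … + 91 = 455 of 29 × 29 × 17 = 14,297 combinations, or 3.2%.
- Onset day 35 after infusion 4 needs g ≤ 65. That occurs in 1 + 2 + 3 + 4 = 10 of 841 combinations, or 1.2%.
- Days 1-60 should equal the mean of days 1-30 and 31-60: (90.3 + 72.8)/2 = 81.6, (8.1 + 61.9)/2 = 35.0, (0 + 17.8)/2 = 8.9. All agree.
- Days 61-89 follow from (59 × share for 31-89 − 30 × share for 31-60)/29, giving about 29% / 34% / 70%.

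The last line shows why the 31-89 row should not be read alone: low coverage on days 31-60 after infusion 4 is offset by high coverage on days 61-89.

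**The case against.** The strongest reply is that confirmatory sampling triggered by clinical suspicion is a legitimate design. Part (a) already needs recognized signs, so an unrecognized event fails whatever the draw schedule. A recognized one has a route to a sample: the 14-day call, an unscheduled visit that must take place if clinically indicated, and 13.1.5, which permits a DSA draw on suspicion of this very syndrome and points to the definition. Adjudication support also exists outside the protocol: "Sites will be provided instructions in the MOP on how to collect and submit event information required for CEC review". The Manual of Procedures, the Clinical Events Committee charter and the Laboratory Manual are not available here, and any of them might make the draw mandatory.

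Much of this stands. It limits what can be said about the number of cases lost. It does not close the gap in the protocol and SAP text, because no visible passage turns the permission into a requirement or puts DSA among the unscheduled-visit assessments.

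Three stronger readings are tempting and not supported.

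- A reader might take 8% or 0% coverage to mean that 92% or 100% of early cases would be missed. The figures exclude for-cause draws and assume uniform timing, so they measure the schedule and not missed cases.
- A reader might infer that such events disappear from the safety data. They are still captured as adverse events, and count toward other primary safety endpoints if serious or judged related to product or procedure.
- A reader might infer from the days 31-89 averages (51% / 48% / 44%) that the infusions differ only in the first 30 days. The days 31-60 row shows that the shortfall after infusion 4 lasts to about day 60.

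**Conclusion.** The point holds as a gap in how one primary safety endpoint is confirmed. At nominal timing, onset before day 30 after infusions 2-3, or before day 60 after infusion 4, can meet part (b) only through a for-cause draw (or an early-termination draw, if one happens to fall in the window). For infusion 4 this is true of any onset before day 32 even at the window extremes. After infusions 2-3 the wider windows give some scheduled cover, averaging 8.1% over onset days 1-30. The day bounds rest on the protocol's own windows; the percentages also rest on uniform visit timing and equally weighted onset days.

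The syndrome may therefore be under-counted after the repeat infusions. The documents do not show by how much, because they do not show how often a suspected case would go unsampled. A low or zero count after infusions 2-4 should be read with that limit in mind. It is not evidence that cases were missed. SAP Appendix F is blacked out, so the absence of a DSA threshold table can be stated only for the visible text.

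**What to change.** 1. **Protocol 13.1.5.** For any remaining follow-up, require rather than permit a DSA sample within the definition's own 30 days of onset whenever the syndrome is clinically suspected. The cost is an occasional draw that the protocol already allows. It still depends on the Investigator's suspicion and cannot reach past infusions. It has no effect if follow-up is complete, as the SAP Addendum's past-tense account of adjudication suggests it may be.

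2. **SAP 5.7.** Tabulate by arm and visit the number of subjects meeting the part (b) threshold out of those sampled, whether or not a syndrome was recorded. State the MFI rule, because the data are held by donor, allele and HLA class and the definition does not say which value counts. One option is the highest donor-specific MFI per subject and visit, compared with the same measure at baseline. The cost is one table from samples already scheduled; it does not recover missing in-window samples.

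3. **Study report.** State that syndrome counts after infusions 2-4 depend on for-cause sampling for onset before about day 30 (infusions 2-3) or day 60 (infusion 4). The cost is one sentence. A count of suspected cases that could not be evaluated should be left out unless the committee's source review supports it. Protocol 13.2.3 excludes individual signs and symptoms from adverse event reporting, and SAP Addendum 3.1 says that adjudication results were returned only where they differed from the original assessment.

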13.1.6. Clinical Laboratory Assessments

All blood samples are to be collected following the standard institutional procedures for blood and urine collection and submitted to a central laboratory for analysis.

Instructions on collection, processing, storage and shipping the samples to the central laboratory are located in the Laboratory Manual.

13.1.6.1. Hematology

Hematological testing will include complete blood count (CBC) with white blood cell (WBC) differential, hemoglobin, hematocrit and platelet count

13.1.6.2. Serum Chemistry

Serum chemistry testing will include: basic metabolic panel (Glucose, Sodium, Potassium, Chloride, Bicarbonate, BUN, Creatinine, Calcium), comprehensive hepatic panel (Albumin, Alkaline Phosphatase, Total Protein, ALT, AST, GGT, Direct Bilirubin, Total Bilirubin), and Creatine Kinase

